Treatment Plan	Patients will be treated with regorafenib 160 mg PO daily for the first 3 weeks of each cycle (1 cycle = 4 weeks) until disease progression. Response evaluation will be every 2 cycles (approximately 2 months) using RECIST v 1.1.
Plan for statistical analysis	Optimal two-stage Simon design. First stage includes 12 patients. If > 3 patients have PFS > 4 months, and additional 19 will be enrolled for a total of 31 patients.

SCHEMA

[figure not shown]

TABLE OF CONTENTS

Synopsis	2
Schema	3
Table of Contents	4
List of Abbreviations	5
1.0 Introduction	6
2.0 Study Objectives	9
3.0 Selection of Subjects	9
4.0 Treatment Plan	12
5.0 Study Procedures	23
6.0 Endpoint Assessment	25
7.0 Adverse Events and Safety Monitoring	28
8.0 Drug Information	33
9.0 Statistical Methods and Determination of Sample Size	34
10.0 Study Management	35
Appendices	
References	40

LIST OF ABBREVIATIONS

ALT	Alanine aminotransferase
aPTT	Activated partial thromboplastin time
AST	Aspartate aminotransferase
BUN	Blood Urea Nitrogen
CR	Complete Response
CTCAE	Common Terminology Criteria for Adverse Events
ECOG	Eastern Cooperative Oncology Group
ERK	Extracellular Signal-regulated Kinases
FDA	Food and Drug Administration
FGFR	Fibroblast Growth Factor Receptor
GCP	Good Clinical Practice
GMP	Good Manufacturing Practice
HFSR	Hand-foot-skin reaction
IB	Investigator's Brochure
ICF	Informed Consent Form
ICH	International Conference on Harmonisation
IRB	Institutional Review Board
MAPK	Mitogen Activated Protein Kinase
PD	Progressive Disease
PDGFR- β	Platelet Derived Growth Factor Receptor-beta
PFS	Progression-free survival
PO	per oris , oral
PR	Partial Response
PS	Performance Status
PT/INR	Prothrombin time/ International Normalized Ratio
QD	quaque die , once daily
RAF	Rapidly Accelerated Fibrosarcoma
RAS	Rat sarcoma
RECIST	Response Evaluation Criteria for Solid Tumors
SAE	Serious Adverse Event
SD	Stable Disease
TK	Tyrosine Kinase
TTP	Time to Progression
VEGF	Vascular Endothelial Growth Factor
VEGFR	Vascular Endothelial Growth Factor Receptor

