4.0 TREATMENT PLAN

4.1 OVERVIEW

The eligible study population will consist of adult patients with histologically confirmed, measurable, unresectable or metastatic angiosarcoma who have progressive disease after prior treatment with ifosfamide, doxorubicin or a taxane. Patients will be treated with daily oral regorafenib (160 mg) for 3 weeks on followed by 1 week off (1 cycle = 4 weeks). Patients will continue treatment until disease progression or withdrawal due to unacceptable toxicity. Once off-treatment, patients will be followed for overall survival up to 5 years. An optimal two-stage Simon design will be employed. The first stage will include 12 patients. If > 3 patients achieve a PFS > 4 months, an additional 19 patients will be enrolled for a total of 31 patients.

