6.2 PRIMARY ENDPOINT ASSESSMENT

The primary endpoint of the study will be progression-free survival (PFS) at 4 months, defined as the absence of progression at 4 months. Patients must complete at least 2 cycles of study treatment to be considered evaluable for this endpoint.

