6.3 SECONDARY ENDPOINT ASSESSMENT

The progression-free rate (PFR) at 3 and 6 months will be defined as the number of patients with progression absent at these timepoints divided by the total number of study patients. Median PFS (defined as the duration of time from start of treatment until time of progression or death, whichever occurs first) will be estimated as a secondary endpoint. Overall survival will be defined as the time from start of treatment until death by any cause. Response rate (by RECIST v 1.1) will be calculated using the definitions above. The rate and duration of tumor control will be defined as the number of CR+PR+SD responses. Patients must complete at least 2 cycles of study treatment to be considered evaluable for efficacy endpoints.

To evaluate the safety and tolerability of regorafenib, all subjects who receive at least one dose of study treatment will be considered evaluable for the safety analysis. Safety variables will include the following: AEs, laboratory changes (complete blood counts, electrolytes, chemistry, and coagulation), changes in vital signs (blood pressure, heart rate, respiratory rate, and temperature) and results of clinically indicated studies outside study guidance, such as ECG or chest x-ray images, as produced at the investigator’s discretion. All AEs whether considered drug-related or not, will be reported with a diagnosis, start/stop dates, action taken, whether treatment

was discontinued, any corrective measures taken, outcome, and other possible causes. For all events, the relationship to treatment and the intensity of the event will be determined by the investigator. All observations pertinent to the safety of the study treatment will be recorded and included in the final report. This trial will use the NCI CTCAE v 4.0 criteria for assessment of toxicity and SAE reporting with regard to toxicity grade.

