9.3 TRIAL DESIGN AND DETERMINATION OF SAMPLE SIZE

A two-stage optimal Simon design will be employed to test the null hypothesis that the probability of progression-free survival of 4 months or greater (P) is ≤ 0.22 versus the alternative that the probability ≥ 0.45 . To test this hypothesis with adequate power, a first stage involving 12 patients will be completed. If > 3 patients achieve progression-free survival of 4 months, the trial will be continued for a total of 31 patients. If > 11 out of 31 patients achieve progression-free survival of 4 months, the trial will reject the hypothesis that $P \leq 0.22$ and conclude that $P > 0.45$,

To determine sample size, the following parameters were employed: $P0 = 0.22$, $P1 = 0.45$, $\alpha = 0.05$ and $\beta = 0.20$. Computations originally performed using software PASS (www.ncss.com).

N1	R1	PET	N	R	Avg N	α	β	Satisfied
26	9	0.000	26	9	26.00	0.043	0.194	Single Stage
7	0	0.176	26	9	22.66	0.042	0.199	Minimax
12	3	0.739	31	10	16.96	0.047	0.188	Optimum

Definitions:

N1 – sample size in the first stage

R1 – drug rejection number in the first stage

PET – probability of early termination of study

N – combined sample size of both stages

R – combined drug rejection number after both stages

Avg N – average sample size if this design is repeated many times

α – probability of rejecting that $P < P0$ when this is true

β – probability of rejecting that $P > P1$ when this is true

P0 – response proportion P of a poor drug

P1 – response proportion P of a good drug

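### Sections 6.2 and 6.3 leave patients who do not complete 2 cycles out of the efficacy analysis, so reported rates are likely biased upward, and section 9.3 does not reconcile this with 12 and 31 enrolled patients

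*Combined protocol and SAP*

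**What the plan says.** - **Primary endpoint (6.2).** The endpoint is absence of progression at 4 months; death is not named. Then: "Patients must complete at least 2 cycles of study treatment to be considered evaluable for this endpoint".
- **Secondary endpoints (6.3).** The section closes its efficacy paragraph with "Patients must complete at least 2 cycles of study treatment to be considered evaluable for efficacy endpoints". Earlier in that paragraph the 3- and 6-month progression-free rates are "divided by the total number of study patients". PFS runs from start of treatment to progression or death, and "Overall survival will be defined as the time from start of treatment until death by any cause".
- **Safety set (6.3).** Everyone who receives at least one dose.
- **Treatment duration (4.1, 4.2).** "Patients will continue treatment until disease progression or withdrawal due to unacceptable toxicity". A cycle is 28 days, so 2 cycles are 56 days.
- **Sample size.** After 12 first-stage patients, section 4.1 says "an additional 19 patients will be enrolled for a total of 31 patients", and the synopsis agrees: "additional 19 will be enrolled for a total of 31 patients". The text of 9.3 gives the final rule as "If > 11 out of 31 patients achieve progression-free survival of 4 months", while its table lists R = 10. Section 9.3 does not mention evaluability.
- **Analysis (9.4).** No efficacy analysis set is defined.

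**The concern.** Completing 2 cycles is a post-baseline event tied closely to the outcome. Three groups leave the efficacy set:

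1. Patients who die before completing 2 cycles.
2. Patients whose progression is documented before then. Groups 1 and 2 are both 4-month failures under the PFS definition in 6.3.
3. Patients who stop early for toxicity, or for symptomatic deterioration without objective progression (6.1.4). They leave whatever their 4-month status would have been.

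No section counts any of them as failures. In a single-arm trial judged against a fixed 22%, no control arm shares the selection, so it passes straight into the reported estimates. For PFS and OS, whose clocks start at first dose, every patient analysed has by construction survived about 8 weeks. That is guaranteed-survival (immortal-time) selection.

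The 4-month primary rate would also rest on a different denominator from the 3- and 6-month rates on either side of it. Two analysts following the text could report different primary rates from the same data.

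**Working it through.** **Inputs.** From 9.3: P0 = 0.22, P1 = 0.45, n1 = 12, r1 = 3, n = 31, and R = 10 (table) or a rule of more than 11 (text). Both cut-offs are carried through; the mismatch between them is a separate matter. The share of patients excluded, x, and the share of those who would truly be progression-free at 4 months, s, are not in the protocol, so ranges are shown.

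**Step 1: reproduce the design.** Rejection probability = sum over x1 = 4 to 12 of b(x1; 12, p) × P(X2 ≥ R + 1 − x1 | 19, p).

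| Quantity | Table in 9.3 | Recomputed, >10 | Recomputed, >11 |
|---|---|---|---|
| Early termination at 0.22 | 0.739 | 0.7390 | 0.7390 |
| Average N at 0.22 | 16.96 | 16.96 | 16.96 |
| Type I error | 0.047 | 0.0468 | 0.0221 |
| Power at 0.45 | 0.812 (1 − 0.188) | 0.8117 | 0.7519 |

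The table is correct for its own cut-off, provided each patient is either a success or a failure.

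**Step 2: effect on the reported rate.** With k successes among N patients, and a share x of them excluded who are all failures, the reported rate is k / [N(1 − x)]. The true rate is multiplied by 1/(1 − x):

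- x = 5%: 1/0.95 = 1.05
- x = 10%: 1/0.90 = 1.11
- x = 20%: 1/0.80 = 1.25

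As an illustration with 3 of 31 excluded, 11/31 = 35.5% becomes 11/28 = 39.3%. The factor is smaller if some excluded patients would have been progression-free at 4 months.

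**Step 3: effect on the decision if 12 and 31 are enrolled patients.** Dropping failures does not change the success count. If non-evaluable patients cannot count as successes, the success probability under the null is 0.22 − x·s, which never exceeds 0.22. Type I error is then at most 0.0468 (>10) or 0.0221 (>11).

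**Step 4: effect if non-evaluable patients were replaced (not provided for anywhere).** The success probability among evaluable patients is p = (0.22 − x·s)/(1 − x). At x = 10%:

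- s = 0 (all failures): p = 0.22/0.90 = 0.244; type I error 8.9% (>10) or 4.7% (>11).
- s = 0.1: p = 0.21/0.90 = 0.233; 6.7% or 3.4%.
- s = 0.22: p = 0.22; no inflation.

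**The case against.** **The decision rule may be untouched.** The synopsis and 4.1 describe 31 enrolled patients, and 9.3 sets a count out of 31. On that reading the error rate is protected. This stands. A reader might infer from 6.2 that the trial's false-positive rate is inflated, but the documents do not support that: no replacement is provided for, so Step 4 is conditional only. Error could also rise if the conclusion rested on the evaluable proportion or its interval rather than on the count, but 9.3 states a count.

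**The bias may be small.** Eligibility asks for life expectancy of at least 4 months and ECOG 0 or 1 (3.1), which limits early deaths. Section 6.1.4 asks for every effort to document progression after discontinuation. Under Table 7, footnote g, the first scan falls in the off week of cycle 2, so progression first found there may still count as 2 cycles completed. Some toxicity stops may be progression-free at 4 months. All of this limits the size, which the documents cannot fix. None of it puts the excluded patients back.

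**The exclusion could appear to change the conclusion.** A reader might note that 11/31 has an exact 95% interval of 19.2% to 54.6%, which includes 22%, whereas 11/26 gives 23.4% to 63.1%, which does not. This carries little weight. At 11 successes the lower limit passes 22% only once at least 4 patients are excluded (11/28: 21.5%; 11/27: 22.4%). The interval is also not the trial's rule: 12/31 meets the text rule, yet its interval is 21.8% to 57.8%.

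**The PFS and OS clocks do not contradict the 2-cycle rule.** A start-of-treatment origin can be applied to a restricted set. The result is selection bias rather than inconsistent text. The real contradiction is within 6.3, over the denominator of the 3- and 6-month rates.

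**Conclusion.** The point holds and should be corrected. As written, 6.2 and 6.3 apply an outcome-dependent evaluability rule that is likely to bias the reported 4-month rate, response rate, tumour control, PFS and OS upward. *Likely* is the right strength: the direction rests on excluded patients doing worse than those retained, and the multipliers in Step 2 assume that all of them are failures. For the 3- and 6-month rates the fault is a contradiction within 6.3, since an all-patient denominator is also stated there.

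Inflation of type I error is not established. It is absent under the enrolled reading with fixed counts, and arises only under practices that the protocol does not describe. Section 9.3 should nevertheless say which patients the 12 and 31 are, because 6.2 leaves that open.

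**What to change.** 1. Delete the 2-cycle requirement for efficacy endpoints in 6.2 and 6.3.
2. Make all registered patients who receive at least one dose the primary efficacy set. This matches the existing safety set.
3. State in 9.3 that 12 and 31 refer to that set, without replacement.
4. In 6.2, count death as well as progression by 4 months as failure, consistent with 6.3.
5. For the Simon count, treat patients with no evidence of being progression-free at 4 months as non-successes. Give a Kaplan-Meier 4-month estimate, with censoring, as a sensitivity analysis.
6. Keep 2-cycle completers as a labelled sensitivity analysis.

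**Cost.** The changes are to text only, with no added patients or visits. If enrolment has begun, they belong in a documented amendment. Reported rates become somewhat lower.

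Item 5 costs some power. Off-treatment follow-up is by phone for survival (Table 7, footnote i), so patients who stop without progression and have no later scan count as non-successes. Some of these will have completed 2 cycles and are evaluable under the current text, so in that respect the new rule is stricter. If 10% of patients stop this way, the success probability at P1 is 0.45 − 0.10·s:

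| Share s who would have been progression-free | Success probability | Power, >10 | Power, >11 |
|---|---|---|---|
| No such stops | 0.450 | 81.2% | 75.2% |
| 0.10 | 0.440 | 78.6% | 71.9% |
| 0.45 | 0.405 | 67.5% | 58.5% |

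The 10% and both values of s are assumptions.

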6.3 SECONDARY ENDPOINT ASSESSMENT

The progression-free rate (PFR) at 3 and 6 months will be defined as the number of patients with progression absent at these timepoints divided by the total number of study patients. Median PFS (defined as the duration of time from start of treatment until time of progression or death, whichever occurs first) will be estimated as a secondary endpoint. Overall survival will be defined as the time from start of treatment until death by any cause. Response rate (by RECIST v 1.1) will be calculated using the definitions above. The rate and duration of tumor control will be defined as the number of CR+PR+SD responses. Patients must complete at least 2 cycles of study treatment to be considered evaluable for efficacy endpoints.

To evaluate the safety and tolerability of regorafenib, all subjects who receive at least one dose of study treatment will be considered evaluable for the safety analysis. Safety variables will include the following: AEs, laboratory changes (complete blood counts, electrolytes, chemistry, and coagulation), changes in vital signs (blood pressure, heart rate, respiratory rate, and temperature) and results of clinically indicated studies outside study guidance, such as ECG or chest x-ray images, as produced at the investigator’s discretion. All AEs whether considered drug-related or not, will be reported with a diagnosis, start/stop dates, action taken, whether treatment

was discontinued, any corrective measures taken, outcome, and other possible causes. For all events, the relationship to treatment and the intensity of the event will be determined by the investigator. All observations pertinent to the safety of the study treatment will be recorded and included in the final report. This trial will use the NCI CTCAE v 4.0 criteria for assessment of toxicity and SAE reporting with regard to toxicity grade.

7.0 ADVERSE EVENTS AND SAFETY MONITORING

This study will be conducted in compliance with the Data Safety Monitoring Plan (DSMP) of the Robert H. Lurie Comprehensive Cancer Center of Northwestern University (please refer to Appendices for additional information). The level of risk attributed to this study requires High Intensity Monitoring, as outlined in the DSMP. In addition, the study will abide by all safety reporting regulations, as set forth in the Code of Federal Regulations and as required by the NCI AdEERS Reporting Guidelines.

Investigators should refer to the Safety Information section of the current IB for regorafenib, including the DCSI (development core safety information), for the expected side effects of regorafenib. As with any agent, there is always the potential for unexpected AEs, including hypersensitivity reactions. The IB will be updated if any new relevant safety data are obtained.

7.1 ADVERSE EVENT MONITORING

Adverse event data collection and reporting, which are required as part of every clinical trial, are done to ensure the safety of subjects enrolled in the studies as well as those who will enroll in future studies using similar agents. Subjects must be carefully monitored for AEs. This monitoring also includes clinical laboratory tests. Adverse events should be assessed in terms of their seriousness, intensity, and relationship to the study drug, or other chemotherapy/treatment. Adverse events are reported in a routine manner at scheduled times during a trial. Additionally, certain adverse events must be reported in an expedited manner to allow for optimal monitoring of patient safety and care.

All patients experiencing an adverse event, regardless of its relationship to study drug, will be monitored until:

- the adverse event resolves or the symptoms or signs that constitute the adverse event return to baseline;
- any abnormal laboratory values have returned to baseline;
- there is a satisfactory explanation other than the study drug for the changes observed; or
- death occurs.

Therapeutic monitoring should be performed following dose modification of regorafenib in a manner consistent with the local clinical standard of care. In general, subjects should be closely monitored for side effects of all concomitant medications regardless of the path of drug elimination.

7.2 DEFINITIONS & DESCRIPTIONS

7.2.1 Adverse event (AE)

An adverse event (AE) is any untoward medical occurrence in a patient receiving study treatment and which does not necessarily have a causal

relationship with this treatment. An AE can therefore be any unfavorable and unintended sign (including an abnormal laboratory finding), symptom, or disease temporally associated with the use of an experimental intervention, whether or not related to the intervention.

7.2.2 Severity of AEs

All adverse events will be graded according to the NCI Common Terminology Criteria for Adverse Events (CTCAE) version 4.0. The CTCAE v. 4 is available at <http://ctep.cancer.gov/reporting/ctc.html>.

If no CTCAE grading is available, the severity of an AE is graded as follows:

- 7.2.2.1 Mild (grade 1): the event causes discomfort without disruption of normal daily activities.
- 7.2.2.2 Moderate (grade 2): the event causes discomfort that affects normal daily activities.
- 7.2.2.3 Severe (grade 3): the event makes the patient unable to perform normal daily activities or significantly affects his/her clinical status.
- 7.2.2.4 Life-threatening (grade 4): the patient was at risk of death at the time of the event.
- 7.2.2.5 Fatal (grade 5): the event caused death.

7.2.3 Serious adverse events (SAEs)

All SAEs, regardless of attribution, occurring during the study or within 30 days of the last administration of study drug must be reported upon discovery or occurrence. Additional expedited or routine reporting may be required, depending on the nature of the SAE (as outlined in 7.3 below). A “serious” adverse event is defined in regulatory terminology as any untoward medical occurrence that:

- 7.2.3.1 Results in death.
If death results from (progression of) the disease, the disease should be reported as event (SAE) itself.
- 7.2.3.2 Is life-threatening.
The patient was at risk of death at the time of the event; it does not refer to an event that hypothetically might have caused death if it were more severe.
- 7.2.3.3 Requires in-patient hospitalization or prolongation of existing hospitalization for ≥ 24 hours.
- 7.2.3.4 Results in persistent or significant disability or incapacity.
- 7.2.3.5 Is a congenital anomaly/birth defect.
- 7.2.3.6 Is an important medical event.
Any event that does not meet the above criteria, but that in the judgment of the investigator jeopardizes the patient, may be considered for reporting as a serious adverse event. The event may require medical or surgical intervention to prevent one of the outcomes listed in the definition of “Serious Adverse Event”.

Examples: allergic bronchospasm requiring intensive treatment in an emergency room or at home; convulsions that may not result in hospitalization; development of drug abuse or drug dependency.

7.2.4 Medical History vs. Adverse Event

- 7.2.4.1 A surgical procedure that was planned prior to the start of the study by any physician treating the subject should not be recorded as AE

(however, the condition for which the surgery is required may be an AE if worsens compared to baseline).

- 7.2.4.2 Conditions that started before registration and for which no symptoms or treatment are present until after registration are recorded as medical history (e.g. seasonal allergy without acute complaints).
- 7.2.4.3 Conditions that started before registration and for which symptoms or treatment are present after registration, *at unchanged intensity*, are recorded as medical history (e.g. allergic pollinosis).
- 7.2.4.4 Conditions that *started or deteriorated after registration* will be documented as adverse events.

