3.2 EXCLUSION CRITERIA

- 3.2.1 Uncontrolled hypertension (systolic pressure >140 mm Hg or diastolic pressure > 90 mm Hg on repeated measurement) despite optimal medical management.

- 3.2.2 Active or clinically significant cardiac disease including:
 - 3.2.2.1 Congestive heart failure – New York Heart Association > Class II
 - 3.2.2.2 Active coronary artery disease
 - 3.2.2.3 Cardiac arrhythmias requiring anti-arrhythmic therapy other than beta blockers or digoxin
 - 3.2.2.4 Unstable angina (anginal symptoms at rest), new-onset angina within 3 months before registration, or myocardial infarction within 6 months before registration
- 3.2.3 Evidence or history of bleeding diathesis or coagulopathy.
- 3.2.4 Any hemorrhage or bleeding event \geq Grade 3 within 4 weeks prior to registration.
- 3.2.5 Subjects with thrombotic, embolic, venous, or arterial events, such as cerebrovascular accident (including transient ischemic attacks), deep vein thrombosis or pulmonary embolism within 6 months of informed consent.
Note: Subjects with recent DVT who have been treated with therapeutic anticoagulating agents for at least 6 weeks prior to study treatment are eligible
- 3.2.6 Subjects with any previously untreated or concurrent cancer unrelated to angiosarcoma. *NOTE: Exceptions include cervical cancer in-situ, treated basal cell carcinoma, or superficial bladder tumor. Subjects surviving a cancer that was curatively treated and without evidence of disease for more than 3 years before registration are allowed. All treatments must have been completed at least 3 years prior to registration.*
- 3.2.7 Patients with pheochromocytoma.
- 3.2.8 Patients with severe hepatic impairment (Child-Pugh Class C)
- 3.2.9 Known history of human immunodeficiency virus (HIV) infection or current chronic or active hepatitis B or C infection requiring treatment with antiviral therapy.
- 3.2.10 Ongoing infection > Grade 2.
- 3.2.11 Evidence of significant central nervous system disease including seizure disorder requiring medication, symptomatic metastatic brain or meningeal tumors.
- 3.2.12 Presence of a non-healing wound, non-healing ulcer, or bone fracture.
- 3.2.13 Renal failure requiring hemo-or peritoneal dialysis.
- 3.2.14 Dehydration > Grade 1.
- 3.2.15 Interstitial lung disease with ongoing signs and symptoms at the time of registration.
- 3.2.16 Pleural effusion or ascites that causes respiratory compromise (\geq Grade 2 dyspnea).

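### Section 7.2.4.2, as worded, lets a silent pre-existing condition that first becomes symptomatic on study be filed as medical history, in conflict with 7.2.4.4

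*Combined protocol and SAP*

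**What the plan says.** Section 7.2.4 tells sites how to sort pre-existing conditions into medical history or AE. It has four items.

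- 7.2.4.1: surgery planned before the study "should not be recorded as AE", but the underlying condition may still be one if it gets worse than at baseline.
- 7.2.4.2: "Conditions that started before registration and for which no symptoms or treatment are present until after registration are recorded as medical history". The example given is "seasonal allergy without acute complaints".
- 7.2.4.3: a condition that began earlier and is symptomatic or treated after registration is history if this is "at unchanged intensity".
- 7.2.4.4: a condition that "started or deteriorated after registration" is documented as an AE.

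The general definition in 7.2.1 reads "An adverse event (AE) is any untoward medical occurrence in a patient receiving study treatment", and it applies "whether or not related to the intervention". It makes no exception for pre-existing conditions. Under Section 3.0, dosing cannot start before registration, so all time on drug falls after registration.

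**The concern.** The word 'until' implies that symptoms or treatment do appear, and that they appear after registration. So 7.2.4.2 assigns to medical history the very case that 7.2.4.4 assigns to AEs: a silent condition that becomes symptomatic on study.

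Safety and tolerability form a secondary objective (Section 2.2), and the safety analysis in Sections 6.3 and 9.4 rests largely on AEs. AEs are graded (7.2.2), documented with relationship, action and outcome (7.3.3), and routinely reviewed by the Data Monitoring Committee (DMC) (7.3.1). Table 7 schedules medical history at screening only, so a flare filed there would have no scheduled on-treatment follow-up as history.

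Patients with silent conditions can enter. Section 3.2 excludes several conditions only when active or symptomatic: for example, 3.2.11 names "symptomatic metastatic brain or meningeal tumors", 3.2.15 requires ongoing signs and symptoms of interstitial lung disease, and 3.2.2.2 requires active coronary disease. With six listed centers, sites may classify the same event differently.

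**Working it through.** No sample size, power or error rate bears on this point, and the plan gives no figure to reproduce. The check is to run four cases through the rules.

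| Condition began before registration and is... | 7.2.4.2, literal wording | 7.2.4.3 | 7.2.4.4 and 7.2.1 | Result |
|---|---|---|---|---|
| A. Silent before, silent after | Fits the example; fits the word 'until' poorly | Does not apply | No untoward occurrence | History |
| B. Silent before, symptomatic after | **History** | Does not apply: intensity has changed | **AE** | **Conflict** |
| C. Symptomatic before, same after | Does not apply | History | Not deteriorated | History |
| D. Symptomatic before, worse after | Does not apply | Does not apply: intensity has changed | AE | AE |

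1. **The conflict is confined to case B.** Going from no symptoms to symptoms is a deterioration, so 7.2.4.4 applies. Once dosing has begun, 7.2.1 applies too. The literal wording of 7.2.4.2 gives the opposite answer, and no order of precedence is stated.
2. **The literal rule gives an odd ordering.** A mild symptomatic condition that worsens (D) is an AE, while a condition that goes from nothing to symptomatic (B) is history. No rationale is given for treating B less strictly than D.
3. **The example belongs to case A.** An allergy without complaints is a condition that stays silent. This suggests that the author meant A and that the wording slipped into B.
4. **The safeguard is missing only here.** Item 7.2.4.1 leaves a route to an AE on worsening, and 7.2.4.3 requires unchanged intensity. Item 7.2.4.2 has neither.
5. **SAEs.** Section 7.2.3 defines seriousness mainly by outcome and requires reporting whatever the attribution, so fatal, life-threatening or disabling flares remain reportable. The one textual route to losing an SAE has two steps: the flare is first filed as history, and the resulting admission is then treated under 7.2.5.3 as not connected to an AE.
6. **Size.** The number of patients affected would be N × (share entering with a silent condition) × (share of those who flare) × (share of flares misfiled). The documents supply only N, which is 31 if the second stage opens and 12 if it does not. None of the three shares is given, so no count can be derived.

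**The case against.** The strongest opposing case is that the section as a whole already captures flares. Item 7.2.4.4 is mandatory and 7.2.1 is broad. Item 7.2.4.2 never says that the event is not an AE, whereas 7.2.4.1 does say so about planned surgery. One can read 7.2.4.2 as covering only the underlying condition and leaving its flare to 7.2.4.4. The example supports that reading.

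There are also backstops. Section 4.3.3 calls hypertension a known AE and requires at least weekly measurement for six weeks, Table 5 grades it, and Section 6.3 lists blood pressure change as a separate safety variable. Appendix IV has the Quality Assurance Monitor (QAM) review each submitted eCRF for toxicities and safety issues and present issues that may affect patient safety to the DMC. For brain metastases, 7.2.3 lists convulsions among its SAE examples.

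Much of this stands. A reader might infer that on-drug flares are systematically kept out of the AE and SAE data. The documents do not support that, because two other provisions still call a flare an AE and SAE reporting is largely independent of the history classification. A reader might also be tempted to turn an assumed prevalence of silent conditions into a count of lost events. That would require every such patient to flare and every flare to be misfiled, and nothing in the documents supports either assumption.

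What does not stand is the view that no correction is needed. The benign reading is possible but is written nowhere. Item 7.2.4.2 is the more specific rule, and a coordinator who follows it to the letter would misclassify case B.

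**Conclusion.** The concern holds as a conflict between two operative classification rules. As worded, 7.2.4.2 and 7.2.4.4 give opposite answers for a pre-existing silent condition that first becomes symptomatic after registration. Some flares could be filed as medical history, inconsistently between sites, and any error would run toward fewer AEs. Whether this happens depends on sites applying the literal wording and on the QAM review not catching it; the documents do not settle either.

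SAE exposure is limited to hospital admissions that pass through 7.2.5.3. The size of the effect cannot be quantified from the documents. The primary endpoint, the stage rules and the sample size are unaffected. The correction is worth making because the protocol's own example supports it and it costs little.

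**What to change.** - Limit 7.2.4.2 to conditions that began before registration and have no symptoms or treatment after it. The existing example then fits.
- Add a sentence stating that 7.2.4.4 governs when a previously silent condition becomes symptomatic, worsens, or needs treatment because of such worsening. Elective or prophylactic treatment without an untoward occurrence should not count as an AE in itself, since 7.2.1 requires an untoward occurrence.
- Have the QAM query existing medical-history entries that show a symptom or treatment start date after registration, and reclassify where 7.2.4.4 applies.

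The cost is a short amendment, a small query of the eCRF data and slightly more recorded AEs. No dosing or clinical management rule changes.
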